8.2 Data Analysis

To analyze the data, descriptive analyses (means, medians, standard deviations, proportions, and frequency distributions) and correlation analyses (Spearman/Pearson rank correlations) will be conducted to assess and describe the cohort. Baseline comparability between study arms will be assessed with parametric and nonparametric analyses including two sample t-tests, Wilcoxon Rank Sum, and Chi-Square tests of proportions. Every effort will be made to keep subjects in the study for the entire follow-up. Analysis will be based on intention-to-treat, regardless of whether the subject completed the intervention program. The primary outcome is the percentage of patients with lipids checked (available now through national laboratory chain) or that reported having their lipids checked. Secondary outcomes include the percentage of subjects that reported initiating LLT, self-efficacy, and patient activation as described above. We will determine these outcomes in each group (self-administered online learning program and the CARE RA arm) as well as differences in these outcomes between the groups. Two-sided t-tests will be used to calculate differences and P values ≤ 0.05 will be considered statistically significant. We will examine differences in socio-demographics, disease severity, and depressive symptoms. These characteristics will be included in a multivariable logistic regression model to determine their association with the outcome (lipids being checked) and potentially increase the statistical power of the test of group differences.

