3. STUDY OBJECTIVES AND OUTCOMES

3.1 Primary Objective

The primary objective is to test the difference in the proportion of subjects who receive cardiovascular risk assessment or learning from their healthcare provider that they already had one in the past year, between subjects randomized to the peer coaching condition and subjects randomized to the self-administered online learning condition.

3.2 Secondary objectives:

To determine whether the CARE RA program is effective in improving the following patient generated health data compared to subjects in the self-administered online learning arm.

1. Change in Routine Assessment of Patient Index Data (RAPID3) score from baseline to the end of the study between arms.
2. Change in Social Support Survey Score from baseline to the end of the study between arms.
3. Change in Patient Activation Measure (PAM) score from baseline to the end of the study between arms.
4. Change in Patient Health Questionnaire – 8 (PHQ-8) score from baseline to the end of the study between arms. Subjects who score a 10 or higher on the PHQ-8 at baseline data collection will be referred to mental health resources and counseling (websites, links, educational materials) by the study team. Peer coaches will be trained to direct subjects who express depressed thoughts and feelings during the course of the program to the mental health resources and counseling and will report such instances to the research team.
5. Change in General Self-Efficacy (GSF) score from baseline to the end of the study between arms.
6. Change in Medication Understanding and Use Self-Efficacy Scale (MUSE) score from baseline to the end of the study between arms.
7. We will examine the feasibility of the intervention by having 80% or more of the subjects complete the intervention.

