Individuals who are interested in participating will respond to the research assistant's contact information on the invitations for ArthritisPower, the survey that Bendcare is administering, and BuildClinical flyers and corresponding survey. An unblinded research assistant from WCM will respond to direct emails from interested individuals to schedule a screening telephone call. The WCM research assistant will also call patients that have indicated on the Bendcare survey, the Twitter REDCap survey, or patients of [name], [name], [name], [name], [name], and [name] who have not marked in EPIC their wish not to be contacted for research. Before the research assistant calls the participants, they will text them from a secure number through Doximity to let them know that they will be calling them shortly. During this phone call, the study will be explained in full. Prior to any study activities, subjects will be screened for eligibility and if eligible, they will review with the unblinded WCM research assistant the Informed Consent form approved by WCM Institutional Review Board (IRB) and which complies with regulatory requirements. Subjects will be given adequate

[figure not shown]
time to consider any information concerning the study given to them by the Investigator or designee. As part of the Informed Consent process, subjects will be given the opportunity to ask the Investigator any questions regarding potential risks and benefits of participation in the study. This informed consent process will be voice recorded during the screening telephone call in the secure HIPAA protected server of WCM Division of General Internal Medicine.

Enrollment and Randomization

We will randomize subjects by a computer-generated random allocation list. The unblinded research assistant will call the subject to complete the enrollment and randomization in the study. The call will consist of the following activities:

- The subject will need to provide the date of their next appointment with their rheumatologist or other physician on their care team .
- The intervention will begin at least 6 weeks before their next appointment and the first data collection point will be at that time.
- Once a subject is enrolled and randomized, the unblinded research assistant will inform the subject the arm they have been assigned to (CARE RA vs self-administered online learning) by phone.

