We will use REDCap to collect the data at baseline, post-intervention, and final follow up. The subject will receive a REDCap link via email that they will click to access the surveys at each data collection point. A blinded research assistant from WCM will follow up by phone with those subjects that have not completed or partially completed the surveys to minimize missing data.

Session	Objectives	Activity/Assignment	PALS - Renewable Knowledge Objects (RKOs)
1. "Introduction to the CARE RA Program"	
 1. Get to know each other 2. Introduce the CArteriovascular Risk assEssment Program for Rheumatoid Arthritis (CARE RA) program 3. Introduce the client to the Patient Activated Learning System (PALS) 	
 A. Verify contact information and receipt of Activity Book B. Get to know each other C. Introduce the CARE RA program D. Introduce the PALS E. Rules and Responsibilities F. Sign contract G. PALS assignments (RKOs) for Session 2 H. Schedule Session 2 call 	None for Session 1
2. "RA and My Heart"	
 1. Learn how RA affects your heart 2. Learn why a cholesterol test is needed to assess risk for heart attack and stroke 	
 A. Greetings between coaches and clients B. Verify the client has reviewed the RKOs and introduction to Session 2 C. Review of PALS assignments for Session 2 D. CARE RA Highlights of Session 2 E. Plans for Session 3 F. PALS assignments for Session 3 G. Schedule Session 3 call 	
Required:
 
 - How can rheumatoid arthritis (RA) affect my body and my health? - What does atherosclerotic cardiovascular disease (ASCVD) risk mean? - How does rheumatoid arthritis (RA) affect my heart? - How can I lower my risk of heart disease if I have rheumatoid arthritis (RA)? - What is cholesterol? - Do I need a cholesterol test if I have rheumatoid arthritis (RA)? 
Learn more:
 
 - What is rheumatoid arthritis (RA)? - How is rheumatoid arthritis (RA) treated? - What medicines are used to treat rheumatoid arthritis (RA)?

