4. "Requesting Cholesterol Test"	
 a. 1. To describe the importance of having a cholesterol test in order to learn what your risk is for heart attacks and strokes 2. To learn about how to communicate with your doctor about getting your cholesterol checked 3. To provide an overview of the medications used to lower your risk for heart attacks and strokes 	
 A. Greetings between coaches and clients B. Verify that client has reviewed the RKOs and introduction to Session 4 C. Review of PALS assignments for Session 4 D. CARE RA Highlights of Session 4 E. Making a plan: 
 A. Getting cholesterol test 
 - Rheumatologist? - Primary Care Physician? B. Doing something with the results 
 - Who will assess the CVD risk? - Who will manage cholesterol if CVD is high? C. Once you find out you have a test (feasibility): 
 - Make a plan for determining 10-year CVD risk - Make decision for initiation of statins F. Rehearse script to request a cholesterol test G. Plans for Session 5 H. PALS assignments for Session 5 I. Schedule Session 5 call 	
Required:
 
 - How can I talk with my doctor if they are in a rush? - What medications are used to treat high cholesterol? - Do statins lower my chances of blood pressure related problems like heart disease and stroke? - When do I have to start taking medicine to treat high cholesterol? - Can rheumatoid arthritis (RA) medications lower my risk for heart attacks and stroke? - Do I need to prepare for a cholesterol test? 
Learn more:
 
 - Can I take my rheumatoid arthritis (RA) medication with statins? - What are some common side effects of statins?

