5. "How Did it Go?"	
 1. To discuss how the encounter with the rheumatologist or other physician on their care team was regarding having a cholesterol test done 2. To learn more about how exercise and diet can help people with RA lower their cholesterol. 3. To establish plans for follow up with a primary care physician for possible initiation of statins 	
 A. Greetings between coaches and clients B. Verify that client has reviewed the RKOs and introduction to Session 5 C. Review of PALS assignments for Session 5 D. CARE RA Highlights of Session 5 E. Discussion about the visit with the doctor F. Emphasize importance of following up with PCP G. Final questions and closure 
Note: Client should have completed the form with all the information for the 10-year pooled cohort risk equation.
	
Required:
 
 - What foods can help lower my cholesterol? - What is a healthy diet or eating pattern? - Can exercise help my rheumatoid arthritis (RA)? - Does exercise lower my risk for heart attacks and stroke if I have rheumatoid arthritis (RA)? - How can I exercise when I am in pain? - What should I expect when I receive the results of a cholesterol test? 
Learn more:
 
 - Can exercise make my rheumatoid arthritis (RA) symptoms worse? - What foods can help improve my rheumatoid arthritis (RA)? - What are the benefits of exercise?

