7.4 Post-intervention completion data collection point (All subjects in the study)

This call will take place around a week after completing the intervention by the blinded research assistant. This is a data collection call for all subjects in the study.

- **Surveys**
 - RAPID3
 - Social Support Survey
 - Patient Activation Measure (PAM)
 - Patient Health Questionnaire – 8 (PHQ- 8)
 - The General Self-Efficacy Scale (GSF)
 - Medication Understanding and Use Self-Efficacy Scale (MUSE)
- **Outcomes**
 - Cholesterol test
 - Initiating lipid lowering therapy
- **Program Evaluation**
 - Evaluation Survey
 - Focus Group/Interview

7.10 3-month post-intervention completion data collection point (All subjects in the study)

This call will take place around 3 months from completing the intervention by the blinded research assistant. This is a data collection call for all subjects in the study.

- **Complete patient generated health data (PGHD)**
 - RAPID3
 - Social Support Survey
 - Patient Activation Measure (PAM)
 - Patient Health Questionnaire – 8 (PHQ- 8)
 - The General Self-Efficacy Scale (GSF)
 - Medication Understanding and Use Self-Efficacy Scale (MUSE) Outcomes

- **Outcomes**

- Cholesterol test
- Initiating lipid lowering therapy

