8. ANALYSIS AND STATISTICS

8.1 Power Calculations and Sample Size

The primary outcome measure is the percentage of patients in each arm that had a lipid panel checked or initiated LLT. Assuming 80% of the subjects in the intervention group have their lipids checked within the 3 months of the study, and 60% of the subjects in the control group have their lipid checked N=64 subjects per group would have at least 80% power to detect a margin difference of 20%, for a one-sided test and significance level of 0.05. We recognize that the sample of 128 subjects is modest, which reflects the pilot nature of the study in the context of a training grant. We will use data from this pilot study to design a more definitive trial powered to detect smaller differences in the primary outcome, and to compare usual care with the intervention.

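### A self-report alone counts as a primary-outcome success, subjects know their arm, and no planned analysis would show whether over-reporting differs between arms

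*Combined protocol and SAP*

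**What the plan says.** Section 8.2 states: "The primary outcome is the percentage of patients with lipids checked (available now through national laboratory chain) or that reported having their lipids checked". The two sources are joined by an or, so either is enough. The document does not ask for a result or chart record to support a self-report, does not rank the sources, does not say how a conflict between them is settled, and plans no analysis by source. Table 2 and the two follow-up sections list the cholesterol test as an outcome without naming where the information comes from.

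On who reports: at enrolment (section 5.4), "the unblinded research assistant will inform the subject the arm they have been assigned to". On data capture (section 7.2): "The subject will receive a REDCap link via email that they will click to access the surveys at each data collection point". A blinded assistant phones subjects whose surveys are incomplete, and of the post-intervention contact section 7.4 says: "This call will take place around a week after completing the intervention by the blinded research assistant".

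On the difference between arms, the CARE RA session schedule (after section 7.2) includes in Session 4: "Rehearse script to request a cholesterol test". Session 5 has the coach discuss the doctor's visit, and notes: "Client should have completed the form with all the information for the 10-year pooled cohort risk equation". Under sections 4.3 and 6.2, controls receive the full list of the same learning modules and two staff calls. Those calls steer clear of the learning content unless the subject asks.

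The primary outcome is worded differently elsewhere. Section 3.1 also counts "learning from their healthcare provider that they already had one in the past year", and section 8.1 says: "The primary outcome measure is the percentage of patients in each arm that had a lipid panel checked or initiated LLT". Neither adds a verification step.

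**The concern.** When an outcome can be met by the subject's own statement and the subject knows the arm, errors in that statement need not be equal between arms. Here the coached arm is trained in the behaviour being measured and then asked by the coach how it went. Controls have no coach rehearsal and no coach debrief. If this leads some untested coached subjects to report a test, the excess is counted as efficacy.

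Error that differs by arm does not average out with more subjects; it moves the estimated difference. Section 8.1 says the pilot data will be used to design a more definitive trial, so an inflated difference would carry forward. The plan names an objective source, the laboratory chain, but merges it with self-report, so the reader could not see how much of a difference rests on unconfirmed statements.

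**Working it through.** **Inputs from the document.** Section 8.1: 80% v 60%, 64 per arm, one-sided 0.05, at least 80% power. Section 8.2: two-sided 0.05. The document gives no over-reporting rate and no laboratory capture rate, so both are assumed below.

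**Step 1: the plan's own figure.** With pooled variance and no continuity correction,

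n = [1.645 × √(2 × 0.70 × 0.30) + 0.842 × √(0.80 × 0.20 + 0.60 × 0.40)]² / 0.20² = (1.066 + 0.532)² / 0.04 ≈ 63.9, so 64 per arm.

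One-sided power at 64 is 80.1%, so the sample-size arithmetic reproduces. Two-sided power is 69.9%; the conflict over sidedness is a separate matter.

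**Step 2: over-reporting with no true effect.** Let true testing be 60% in both arms and let a share f of untested subjects report a test. The apparent rate is 0.60 + 0.40f. About 0.40 × 64 = 25.6 subjects per arm are untested, so f = 10% is about 2.6 people and f = 25% about 6.4. Rejection rates come from exact binomial enumeration of the pooled z-test at 64 per arm.

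| f, CARE RA | f, control | Apparent rates | Spurious difference | Two-sided 0.05, either direction | One-sided 0.05 |
|---|---|---|---|---|---|
| 0 | 0 | 60% v 60% | 0 | 5.4% | 4.8% |
| 10% | 0 | 64% v 60% | 4 points | 8.0% | 11.9% |
| 25% | 0 | 70% v 60% | 10 points | 22.6% | 33.1% |
| 25% | 10% | 70% v 64% | 6 points | 11.4% | 18.4% |

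Of the 8.0%, 0.8 points are rejections against CARE RA.

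**Step 3: the same thing in counts.** Take 38/64 positive in control (59.4%) and k extra in CARE RA, with z = (k/64) / √(2p̄(1 − p̄)/64), where p̄ is the pooled proportion. At k = 9, z = 1.68, above 1.645. At k = 11, z = 2.08, above 1.96. A lead of 9 reports (one-sided) or 11 (two-sided) decides the test, so a few unconfirmed reports can matter when the observed lead is near those values.

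**Step 4: equal over-reporting works the other way.** With true rates 80% v 60% and f = 20% in both arms, the apparent rates are 0.80 + 0.20 × 0.20 = 84% and 0.60 + 0.40 × 0.20 = 68%. The difference shrinks from 20 to 16 points and one-sided power falls to 68.5%. The concern is therefore confined to over-reporting that differs by arm.

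**Step 5: what a laboratory-only count can do.** If records capture 80% of true tests equally in both arms, 80% v 60% becomes 64% v 48%, and two-sided power at 64 per arm is 44.5%. At 90% capture it is 56.0%.

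**Step 6: why a reported value should not count as confirmation.** Suppose nobody over-reports, true testing is 60% in both arms, and 90% of tested coached subjects but 70% of tested controls can supply a value. These shares are assumed. The confirmed rates are 0.60 × 0.90 = 54% v 0.60 × 0.70 = 42%, and the two-sided test rejects 26% of the time with no true difference.

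**The case against.** The strongest reply is that the documents give no evidence that anyone will over-report. A blinded assistant collects outcomes by the same route in both arms. Controls see the same modules, including those on needing a cholesterol test and on talking to a rushed doctor, so some over-reporting may be shared, and shared over-reporting shrinks the difference. The Session 5 form also cuts the other way: a subject who has written down the risk-equation inputs has a record to report from and may report more accurately. Laboratory data from one chain are incomplete, recruitment is nationwide, and no laboratory record can confirm that a subject learned of a past-year assessment. The study is also a 128-subject pilot.

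Most of this stands as a limit on size. It does not answer the point. Blinding the assistant removes assessor bias but not reporting bias, because the person reporting knows the arm. If the form makes coached reports more accurate, reporting quality still differs by arm, and the plan still cannot show it. Incomplete laboratory data are a reason to keep the composite as primary, but not to leave the sources unseparated. A pilot that feeds a larger trial is a good place to learn how far self-report and records agree.

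A reader might infer that misreporting will favour CARE RA, or that half of untested coached subjects could over-report. The latter would reproduce the full 20-point planned effect with no true difference and reject 70.7% of the time two-sided. The documents support neither: they give no over-reporting rate, and that scenario also requires none among controls.

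**Conclusion.** The point holds as a gap in the plan: a bare self-report is a success, the reporter is unblinded, coaching on the reported behaviour occurs in one arm only, and no analysis would reveal over-reporting that differs by arm. It is not a demonstration of bias. Under modest assumed over-reporting the two-sided rejection rate rises from 5.4% to between 8.0% and 22.6%, or to 11.4% when controls over-report too. These figures rest on a 60% true rate in both arms, 64 analysed per arm, a pooled z-test and assumed fractions. Under the one-sided test of section 8.1 the exposure is larger.

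A reader might also infer that the primary outcome should be replaced by laboratory records. The document does not support that. It does not say that every subject's tests can be found through the laboratory chain, and the laboratory-only count loses power quickly as capture falls. The change is worth making because it should be modest and leaves the primary outcome and sample size as they are.

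**What to change.** In section 8.2:

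1. Keep the composite as primary.
2. Check the laboratory-chain source already named there in the same way for both arms, whatever the subject reported, wherever access and consent allow.
3. Record the source of each positive (laboratory record, self-report only, or both) and tabulate it by arm.
4. Pre-specify a sensitivity analysis that counts laboratory-confirmed tests only.
5. Ask the same questions in both arms on the date of the test and who ordered it, for description. Do not use possession of a cholesterol value to define a confirmed test, because only CARE RA clients are told to complete the risk-equation form.

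The cost is a few data fields, one analysis, one table and the record checks. The effort of those checks cannot be judged from the document, which does not give the access terms; the consent pages are not in the reviewed text. The laboratory-only count misses tests done elsewhere, has about 45% two-sided power if 80% of tests are captured equally in both arms, and cannot confirm the past-year component of section 3.1. The plan should say in advance that it is supportive and that a null result does not overturn the primary.
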